# Participants with elevated ALT ( $> 1.5 \times ULN$ ) at baseline

- ALT < 2 × baseline and bilirubin not elevated (Non-Gilbert: Not elevated = total bilirubin < 2 × ULN. Gilbert: Not Elevated = direct bilirubin < 2 × baseline and INR  $\leq$  1.5)
- ALT < 2 × baseline and bilirubin elevated (Non-Gilbert: Elevated = total bilirubin  $\geq$  2 × ULN. Gilbert: Elevated = direct bilirubin  $\geq$  2 × baseline or INR > 1.5)
- ALT  $> 2 \times$  baseline and bilirubin not elevated
- ALT  $> 2 \times$  baseline and bilirubin elevated
- ALT  $> 3 \times$  baseline and bilirubin not elevated
- ALT  $> 3 \times$  baseline and bilirubin elevated
- ALT  $> 5 \times$  baseline and bilirubin not elevated
- ALT  $\geq$  5 × baseline and bilirubin elevated
- (repeat same categories with AST instead of ALT)

Evaluation of drug-induced serious hepatotoxicity (eDISH) plots of the maximum ontreatment (peak) TBL versus peak ALT or AST will be provided by treatment. Additionally, a cholestatic DILI screening plot will be provided plotting peak on-treatment TBL versus peak on-treatment ALP.

#### 4.5.4 **Vital Signs**

#### 4.5.4.1 **Definitions and Derivations**

Vital signs include SBP (mmHg), DBP (mmHg), heart rate (bpm), respiratory rate (breaths per minute), and temperature (°C). The mean of triplicate blood pressure measurements will be analyzed.

Additionally, vital signs values will be classified as normal (if value is within normal reference range), low (if value is below the normal reference range), and high (if value is above the normal reference range) according to the normal reference ranges (Table 11).

Table 11 **Vital Sign Normal Reference Ranges** 

Parameter	Normal Reference Ranges
Systolic blood pressure	80 - 130 mmHg
Diastolic blood pressure	50 - 80 mmHg
Heart rate	50 - 100 bpm
Respiratory rate	12 - 20 breaths per minute
Temperature	≤ 37.0 °C

#### 4.5.4.2 **Presentations**

Vital sign tables, graphs, and listings will be based on the on-treatment data only in the safety population and presented for each treatment group.

Vital sign results will be summarized with n, mean, SD, median, minimum, and maximum by treatment, and analysis visit and for change from baseline. A frequency table will present number of participants reporting at least 1 treatment-emergent abnormality (result outside of reference range). Low and high abnormalities for the same vital sign will be summarized separately. Observed values and change from baseline in SBP and heart rate measurements will be also presented in figures with mean and standard error of the mean.

All vital sign data will be listed. The listing will include reference ranges and classification of vital signs as normal, low, and high.

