Urine for albumin and creatinine	X			X			X			X	X	
HbA1c (Section 8.1.5)	X			X			X			X	X	
Fasting serum lipid panel (Section 8.1.5)	X									X	X	
Pre-dose blood for PK analysis (Section 8.4)	X	X		X			X			X	X	X
Serum for immunogenicity (ADA) (Section 8.4.2)	X	X		X			X			X	X	X
Blood sampling for ELF (Section 8.1.5)	X									X	X	

Table 4 Schedule of Activities for Part A: Treatment Period and Follow-up

				ŗ	Freatmen	nent Period						
Week	0	4	8	12	16	20	24	32	40	48		Follow-up
Visit	V2	V3	V4	V5	V6	V7	V8	V9	V10	V11 (EOT)	Visit b 4 weeks after EO	4 weeks after EOT or E/D (± 5d) a
Day	1	29	57	85	113	141	169	225	281	337		
(visit window $\pm x$ days) a	1	± 5d	± 5d	± 5d	± 5d	± 5d	± 5d	± 5d	± 5d	± 5d		
Blood sampling for Pro-C3 (Section 8.1.5)	X									X	X	
FIB-4 computed score (Section 8.1.5)	X									X	X	
Blood for fasting plasma glucose-(Section 8.1.5)	X									X	X	
Blood for C-peptide (Section 8.1.5)	X									X	X	
Blood for adiponectin (Section 8.1.5)	X									X	X	
Genomics Initiative optional, exploratory genetic sample (Section 8.6, Appendix D) °	X											
Optional biomarker serum sample (for biomarker research) (Section 8.5.2)	X									X	X	

Participants should withhold alcohol and refrain from intense exercise for 24 hours prior to each study site visit.

- Visit windows should be calculated from Day 1. Visit 2 (randomization) may be scheduled any day following confirmation that participant meets all eligibility criteria including eligibility reading from the central pathology review of the biopsy (historical or on-study) sample and laboratory report assessments from the central laboratory (eg, the screening period does not need to be a full 8 weeks). Follow-up visit conducted 4 weeks (± 5 d) after EOT visit or E/D visit. For participants who discontinue study intervention permanently and do not continue with study visits, follow-up visit should be performed 4 weeks (± 5 d) after the E/D visit. For participants who discontinue study intervention early but continue with study visits, follow-up visit should be performed 4 weeks (± 5 d) after the EOT.
- b Performed in event of early discontinuation of study intervention or withdrawal from study.
- c Activities related to demonstration and training on SC administration can be conducted at Visit 1 and/or prior to randomization at Visit 2.

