# 3.3.1.2 Definition of On-study and On-treatment

All adverse events (AEs) with start date on or after the date of first treatment will be considered on-study. On-treatment AEs are those occurring within the on-study period and within + 7 days of treatment discontinuation. All AEs leading to discontinuation of IP will be considered on-treatment.

On-study assessments (eg, vital signs, clinical laboratory tests, ECG) are defined as those occurring after the date and time (if available) of administration of the first dose of IP. On-

treatment assessments are defined as those occurring within the on-study period and on or before the date of administration of the last dose of IP with the following windows following treatment discontinuation:

- Fasting plasma glucose (FPG): +1 day from treatment discontinuation.
- Biopsy, liver tests (alanine aminotransferase [ALT], aspartate aminotransferase [AST], total bilirubin [TBL], and alkaline phosphatase [ALP]), and disease-specific biomarkers: + 30 days from treatment discontinuation.
- All other efficacy and safety: +7 days from treatment discontinuation.

Assessments other than AEs recorded on the day of first treatment and with time unavailable for the assessment or for the first dose, will be considered to be not in the on-study/on-treatment periods. For listings of AEs, analysis phase will be indicated as on-treatment if the AE starts within the on-treatment period, as 'pre-treatment' if it starts prior to the on-treatment period, and as 'post-treatment' if it starts after the on-treatment period.

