#### 3.3.1.4 Handling of Missing Dates

AE start and end date and concomitant medications (CMs) end date are imputed according to the rules described below. Start and end dates of treatment will not be imputed.

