## 3.3.1.4.5 Imputation of Treatment End Date

If date of end of treatment is unknown, it will be imputed as the date of last contact with the patient.

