## 3.3.2 Visit Window

For the purpose of the statistical analysis, study findings are allocated to the analysis visit using analysis visit windows as described in Table 2, Table 3, Table 4, Table 5, Table 6, Table 7, and Table 8. Note, study day 1 refers to the date the participant received the first dose of IP.

Table 2 Analysis Visit Windows, Biopsy

Analysis Visit	Target Day	Day Range
Week 48	337	1 through end of study

Table 3 Analysis Visit Definitions, 12-lead dECG, Vital Signs, Abbreviated Physical Examination

Analysis Visit	Target Day	Day Range
Week 4	29	2-42
Week 8	57	43-70
Week 12	85	71-98
Week 16	113	99-126
Week 20	141	127-154
Week 24	169	155-196
Week 32	225	197-252
Week 40	281	253-308
Week 48	337	309-351
Week 52	365	352-385

dECG, digital electrocardiogram.

Table 4 Analysis Visit Definitions, Clinical Laboratory Assessments Including eGFR and MELD but Excluding Fasting Glucose (Safety)

Analysis Visit	Target Day	Day Range
Week 4	29	2-42
Week 8	57	43-70
Week 12	85	71-98
Week 16	113	99-126
Week 20	141	127-154
Week 24	169	155-196
Week 32	225	197-280

Table 4 Analysis Visit Definitions, Clinical Laboratory Assessments Including eGFR and MELD but Excluding Fasting Glucose (Safety)

Analysis Visit	Target Day	Day Range
Week 48	337	281-351
Week 52	365	352-385

Due to fasting at the Week 48 visit, random glucose will not be presented for the Week 48 analysis visit. eGFR, estimated glomerular filtration rate; MELD, model for end-stage liver disease.

Table 5 Analysis Visit Definitions, Amylase, Lipase, Coagulation

Analysis Visit	Target Day	Day Range
Week 24	169	2-196
Week 32	225	197-280
Week 48	337	281-378

Table 6 Analysis Visit Definitions, Calcitonin, FibroScan, FAST, Agile 3+, BARD, Fasting Serum Lipid Panel, ELF, Pro-C3, FIB-4, Fasting Plasma Glucose (Efficacy), Fasting Glucose (Safety), C-peptide, Adiponectin

Analysis Visit	Target Day	Day Range
Week 48	337	2-378

BARD, BMI, AST/ALT ratio, diabetes; ELF, enhanced liver fibrosis; FAST, FibroScan-ALT; FIB-4, fibrosis-4; Pro-C3, released N-terminal propeptide of type III collagen.

Table 7 Analysis Visit Definitions, PK, and ADA

Analysis Visit	Target Day	Day Range
Week 4	29	2-57
Week 12	85	58-127
Week 24	169	128-253
Week 48	337	254-378

ADA, anti-drug antibody; PK, pharmacokinetic(s).

Table 8 Analysis Visit Definitions, HbA1c, Urine Albumin, Creatinine

Analysis Visit	Target Day	Day Range
Week 12	85	2-127
Week 24	169	128-253
Week 48	337	254-378

HbA1c, hemoglobin A1c.

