### 4.5.5.2 Presentations

ECG tables and listings will be based on the on-treatment data only in the safety population and presented for each treatment group. ECG parameters (except for the overall evaluation) will be summarized with n, mean, median, SD, minimum, and maximum, at each visit and for change from baseline.

Number and percentage of participants within each QTcF interval classes at any time during the on-treatment period will be also reported together with number and percentage of participants within QTcF increase classes at any time during the on-treatment period.

ECG parameters fulfilling potentially clinically significant criteria at any time during treatment will be summarized by treatment.

Overall evaluation will be analyzed as shift from baseline to last value in the on-treatment period.

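### SAP Table 3 gives vital signs and ECG a Week 52 row that on-schedule follow-up readings cannot enter, and SAP Tables 5 and 7 have no follow-up row

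*SAP*

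**What the plan says.** **Schedule.** Protocol 1.3.2.1 (Table 4) places EOT at Day 337 ± 5. It marks vital signs, ECG, safety laboratory tests, amylase, lipase, coagulation, PK and ADA at the follow-up visit. On timing it says: "Follow-up visit conducted 4 weeks (± 5 d) after EOT visit or E/D visit".

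**Analysis windows (SAP 3.3.2).** Table 3, titled "Analysis Visit Definitions, 12-lead dECG, Vital Signs, Abbreviated Physical Examination", ends with the row "Week 52 365 352-385", that is, target Day 365. Table 4 (safety laboratory) has the same row. The last row of Table 5 (amylase, lipase, coagulation) is Week 48, Day 281-378. The last row of Table 7 (PK, ADA) is Week 48, Day 254-378. When several records share a window, the one nearest the target day is used.

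**Data scope.** For vital signs, SAP 4.5.4.2 states: "Vital sign tables, graphs, and listings will be based on the on-treatment data only in the safety population and presented for each treatment group". For ECG, SAP 4.5.5.2 states: "ECG tables and listings will be based on the on-treatment data only in the safety population". SAP 3.3.1.2 sets the limit that applies to both: "All other efficacy and safety: +7 days from treatment discontinuation". Laboratory output, by contrast, uses on-study data (SAP 4.5.3.2).

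**Listings.** SAP 4.5.4.2 restricts the vital-sign listing to on-treatment data and then says that every vital-sign value is listed. SAP 3.3.3 puts scheduled and unscheduled assessments alike into the listings.

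**Promises.** Protocol 9.4.3 plans observed values and change from baseline at each scheduled visit (vital signs) or assessment (ECG) after baseline. SAP section 2 names one departure from the protocol, the per-protocol set, and no other. The primary immunogenicity endpoint (SAP 4.2.1) covers ADA incidence and titer in follow-up as well as on treatment, and SAP 4.4 presents titers by analysis visit.

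**The concern.** Safety is the primary objective, and change from baseline over time in vital signs and ECG is one of the primary assessments. Increased heart rate is an identified risk and QT prolongation a potential one (Protocol 2.3.1). The follow-up visit supplies the planned readings off drug. Under the current text they get no by-visit summary, and it is unclear whether they are even listed. Follow-up titer is named in a primary endpoint but has no row in the table meant to show it. If an EOT sample in Table 5 or 7 is missing, a sample taken about 4 weeks off drug would be shown as Week 48.

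**Working it through.** Inputs: EOT Day 337 ± 5 and follow-up 28 ± 5 days later (Protocol 1.3.2.1); on-treatment limit of +7 days (SAP 3.3.1.2); windows and selection rule (SAP 3.3.2). The last dose is taken as no later than the EOT visit, because unused product is returned there (Protocol 4.1.1).

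1. **Reproduce the Week 52 row.** Target: 337 + 28 = 365, as in Tables 3 and 4. Earliest follow-up: 332 + 23 = 355. Latest: 342 + 33 = 375. Day 355-375 lies inside 352-385, so the row fits the follow-up visit. There are 11 EOT days × 11 follow-up offsets = 121 combinations.

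2. **Vital signs and ECG.** The latest on-treatment day is 342 + 7 = 349, before the row opens on Day 352. For any EOT day, follow-up comes at least 23 days later and on-treatment data stop at 7, a gap of at least 23 − 7 = 16 days. Result: 0 of 121 combinations qualify. The same gap applies when follow-up is counted from an early-discontinuation visit.

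3. **What could still fill the row.** A Day 352 value is on-treatment only if the last dose was on Day 352 − 7 = 345 or later, which is beyond the EOT window (Day 342). The other route is an unknown stop date. SAP 3.3.1.4.5 says "If date of end of treatment is unknown, it will be imputed as the date of last contact with the patient", which could make a follow-up reading count as on-treatment, but SAP 3.3.1.4 says "Start and end dates of treatment will not be imputed".

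4. **Tables 5 and 7, on-schedule completers.** Day 355-375 lies inside both 281-378 and 254-378, so 121 of 121 follow-up samples fall in Week 48. The EOT sample is at most 5 days from Day 337. The follow-up sample is at least 355 − 337 = 18 days away. EOT therefore wins in 121 of 121; if it is missing, the follow-up sample becomes Week 48.

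5. **Table 4, on-schedule completers.** Day 355-375 lies inside 352-385 and the data are on-study, so 121 of 121 reach Week 52. This table is correct for them.

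6. **Participants who stop early and leave.** Example: stop on Day 60, follow-up on Day 88. Day 88 falls in Week 12 of Tables 4 and 7 and Week 24 of Table 5. In Table 7 it is 3 days from target (85) against 25 for the Day 60 sample. In Table 5 it is 81 days from target (169) against 109. In Table 4, Day 60 belongs to Week 8. The follow-up sample is therefore the one shown in all three.

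**The case against.** Restricting vital-sign and ECG tables to on-treatment data is a defensible choice. It matches the endpoints that count abnormalities during treatment. Protocol 9.4 calls itself a summary and leaves technical detail to the SAP. Clinically relevant deterioration is reported as an AE, AEs are collected through follow-up, and AE tables use all on-study events. Raised heart rate and blood-pressure alteration are events of special interest. ADA incidence, titer boosting and persistence can all use follow-up samples. All of this stands, and it confines the harm to by-visit summaries. It does not explain why Table 3 gives these measures a row that on-schedule data cannot reach, or why SAP section 2 is silent.

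One could also say that PK is presented by visit (SAP 4.3.3) rather than by analysis visit, so Table 7 need not govern it. Table 7's title names PK, so this does not help.

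A reader might go further and infer that Tables 4, 5 and 7 wrongly label off-drug samples from early leavers as treatment weeks. The documents do not support calling that an error. The rows are analysis visits counted from first dose, and laboratory tables are on-study by design. Protocol 7.1 encourages participants who stop drug to keep attending, so their off-drug samples enter the same rows. That section also excepts PK sampling after early discontinuation and does not require laboratory samples beyond 30 days. No discontinuation rate or timing is given, so the number affected is unknown.

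Nor is the Week 52 row of Table 3 necessarily unused: the abbreviated physical examination, which includes weight, shares that table.

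**Conclusion.** Wrong as written, limited to descriptive by-visit output, and it should be corrected.

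- No on-schedule follow-up vital sign or ECG (0 of 121) can enter the row that Table 3 provides. This departs from Protocol 9.4.3 without being declared, and the listing rules contradict one another.
- Tables 5 and 7 have no follow-up row. For on-schedule completers every follow-up sample (121 of 121) falls in the Week 48 window, so follow-up ADA titer has no by-visit row.
- The early-leaver pattern is a secondary note, not an error in itself.

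The counts assume visits within their windows and a last dose no later than EOT; the Week 48 selection result also assumes that an EOT sample exists. They are combinations of days, not shares of the approximately 55 participants to be randomized.

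A reader might infer that follow-up safety data are lost. They are not. AE and adjudicated-event tables, ADA incidence and persistence categories, and laboratory treatment-emergent abnormality counts keep them. Counts defined on treatment are unaffected.

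**What to change.** - Keep on-treatment data for the vital-sign and ECG rows through Week 48 and for all counts defined on treatment.
- Add a row named Follow-up (4 weeks after EOT or early discontinuation), assigned by nominal visit and filled from on-study data, for vital signs, ECG and Tables 5 and 7. Use the same row in place of Week 52 in Table 4. Table 3's Week 52 range can stay for the physical examination and weight.
- Do not also count nominal follow-up samples in the Week-n rows.
- State in SAP 4.5.4.2 and 4.5.5.2 that listings include all on-study data.
- Reconcile SAP 3.3.1.4 with 3.3.1.4.5.

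Assignment by nominal visit matters. Passing on-study vital signs and ECGs through Table 3's fixed windows would repair on-schedule completers, but the Day 88 follow-up in the example above would land in Week 12 (Day 71-98). Off-drug laboratory and ADA samples from participants who stop drug but stay would remain in the Week-n rows, as the on-study design intends.

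Cost: SAP wording and a few table rows from data already collected, with no change to study conduct.

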# Objectives and Endpoints: Part A

Table 1 Objectives and Endpoints: Part A

Objectives	Endpoints
Primary/Safety	
To evaluate the safety and tolerability of cotadutide as compared with placebo in participants with non-cirrhotic NASH with fibrosis	Safety and tolerability will be evaluated in terms of AEs, vital signs, clinical and laboratory assessments, and ECG. Assessments related to AEs cover:  Occurrence/Frequency Relationship to IP as assessed by the investigator Intensity Seriousness Death AEs leading to discontinuation of IP AEs leading to dose reduction of IP AEs leading to dose reduction of IP AEs of special interest Adjudicated CV events including MACE, selected liver events, diabetic ketoacidosis, pancreatitis, pancreatic carcinoma, and thyroid carcinoma  Vital signs parameters include SBP, DBP, and pulse. Assessments cover: Observed value Absolute change from baseline values over time Abnormality at least once on treatment  Laboratory parameters include Clinical Chemistry (including MELD score) and Hematology parameters as well as urinalysis. A complete list of parameters is presented in Section 8.2.5. Assessments cover: Observed value Absolute change from baseline values over time Abnormality/Clinically significant abnormality in laboratory parameters at least once on treatment Treatment-emergent increase in hematuria, proteinuria, and glucose in urinalysis defined as change from negative/trace at baseline to ++, +++, or ++++ at any visit after baseline or an increase of at least ++
	Electrocardiogram measurements include heart rate, RR, PR, QRS, and QT intervals. Derived variables cover QTcF.  Assessments cover:
	
 
Observed value
 
Absolute change from baseline values over time
 

		•	ECG parameters fulfilling potentially clinically significant criteria at any time during treatment, including QRS duration > 118 ms, PR interval > 210 ms, RR < 600 ms (resting heart rate > 100 bpm), and RR > 1330 ms (resting heart rate < 45 bpm)  QTcF exceeding 450, 480, and 500 ms at any time during treatment  Change in QTcF at any time during treatment as compared to baseline exceeding 30 ms and 60 ms
•	To assess the immunogenicity of cotadutide	•	Incidence of ADAs to cotadutide and titer during treatment and follow-up
Exp	ploratory		

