#### 2.3.1 Risk Assessment

The current IB has further information on the potential benefits of cotadutide and an assessment of the potential and known risks. Risks associated with cotadutide and with study-related procedures are presented in Table 7 along with mitigation strategies. Additionally, participants will be monitored throughout the study for signs, symptoms, and/or laboratory analyses suggestive of hepatic decompensation. Participants with hepatic decompensation will

be excluded from further participation in this study (Section 5.2) and will be treated immediately according to standard of care. Specified clinical events, including all potential cases of DILI and CV events, will be adjudicated by an external, independent, and blinded events adjudication committee (Section 8.3.10).

Table 7Risk Assessment

Identified and potential risks of clinical significance	Summary of data/rationale for risk	Mitigation strategy							
Cotadutide									
Identified risks associated with cotadutide:  Nausea Vomiting Injection site reactions Increased heart rate  Potential risks include: Alterations in blood pressure QT interval prolongation Anaphylactic-type reactions Skin rash Hypoglycemia (with sulfonylurea, glitinides, and insulin) Diabetic ketoacidosis (following insulin reduction) Acute renal failure secondary to dehydration Pancreatitis Pancreatic carcinoma Thyroid cancer	Potential risks for cotadutide are based on available published data for GLP-1 receptor agonists and glucagon, as well as clinical and nonclinical data.  Some potential risks (pancreatitis, pancreatic carcinoma, thyroid cancer, gallbladder-related disorders) are based solely on GLP-1 agonists as a class finding	
 
Inclusion/exclusion criteria (Section 5.1 and Section 5.2)
 
Safety monitoring (Section 8.2)
 
Uptitration dosing schedule (Section 4.3)
 
Pen device and instruction on proper injection technique (Section 6.2)
 
							

Table 7 Risk Assessment

Identified and potential risks of clinical significance								
Study Procedures								

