#### 4.2.3 Rationale for Endpoints

# 4.2.3.1 Rationale for Primary/Safety Endpoints

Standard safety endpoints will be assessed, including vital signs, ECG, safety laboratory analysis, AEs, and SAEs. Increases in heart rate have been observed in clinical studies conducted to date with cotadutide (studies D5670C00001, D5670C00002, and D5670C00004), accompanied by a trend toward a reduction in BP with repeat dosing. A particular focus on CV safety will involve monitoring of CV events, which will be adjudicated by an external, independent, and blinded events adjudication committee (Section 8.3.10).

The ADA and titer (if participants are ADA positive) will be used to assess potential immunogenicity in NASH.

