#### 9 STATISTICAL CONSIDERATIONS

# 9.1 Statistical Hypotheses

For the primary safety objective, analyses will compare cotadutide treatment to placebo. The exploratory efficacy analyses will test the null hypotheses of no treatment effect for cotadutide versus placebo in the FAS.

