## **9.4.3 Safety**

Safety analyses will be performed using the safety analysis set. Safety data will be presented using descriptive statistics unless otherwise specified and will not be formally tested.

Safety events and findings will be summarized by treatment group. Erroneously treated participants (eg, those randomized to treatment A but actually given treatment B) are accounted for in the treatment group with the majority estimated usage. The majority estimated usage will be determined based on which treatment had more kits dispensed (not including kits returned unused). In the case of a tie, the randomized treatment will be used for safety analyses. In all cases, the dose group will be the same as randomized dose level.

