  - Both total and high molecular weight adiponectin will be assessed
- Change from baseline in SBP through Week 48

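### Heart rate, an identified risk, and QTcF are summarised by arm only: the SAP specifies no difference from placebo, no interval for one, and no baseline adjustment

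*SAP*

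**What the plan says.** **The question.** Protocol Table 1 states the primary objective as "To evaluate the safety and tolerability of cotadutide as compared with placebo in participants with non-cirrhotic NASH with fibrosis". Protocol 9.1 adds: "For the primary safety objective, analyses will compare cotadutide treatment to placebo". Protocol 9.4.3 sets the style of analysis: "Safety data will be presented using descriptive statistics unless otherwise specified and will not be formally tested".

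**The risk.** In Protocol 2.3.1 the identified risks read "Nausea Vomiting Injection site reactions Increased heart rate", so heart rate is the only cardiovascular item among them. The potential risks include "Alterations in blood pressure QT interval prolongation". Protocol 4.2.3.1 gives the background: "Increases in heart rate have been observed in clinical studies conducted to date with cotadutide".

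**What heart rate and QTcF receive.**
- Vital-sign heart rate (SAP 4.5.4.2): n, mean, SD, median and range by arm and visit, for values and changes; counts of low and high treatment-emergent abnormalities; and a plot, described as "change from baseline in SBP and heart rate measurements will be also presented in figures with mean and standard error of the mean".
- Increased heart rate as an AESI (SAP 4.5.2): counts of participants by arm.
- ECG heart rate and QTcF (SAP 4.5.5): the same kind of summary statistics, counts of short and long RR intervals, and counts of QTcF above 450, 480 and 500 ms and of increases around 30 and 60 ms.

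**What SBP receives.** As a safety vital sign, SBP is treated exactly like heart rate. It is also listed in SAP 4.2.3.1 as an exploratory endpoint: "Change from baseline in SBP through Week 48". That brings in the MMRM of SAP 4.2.3.4, which adjusts for baseline, fibrosis stage, T2DM status and visit, uses on-treatment data, and reports 95% CIs.

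**The concern.** The plan sets out to judge safety against placebo, and heart rate is the cardiovascular effect already established for this drug. Yet no output for heart rate or QTcF puts a number on cotadutide minus placebo, and none uses the baseline values that are collected anyway. SBP comes from the same visits and the same vital-sign set, and it is modelled.

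About 55 participants are split over two doses and placebo, so arms can differ at baseline by chance. A reader who wants the placebo-corrected heart-rate effect must build it from the tables, without adjustment. At stake are the clarity and precision of one of the few safety effects that this small study can estimate on a continuous scale.

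**Working it through.** **Plan's own figure.** The documents give no precision figure for heart rate or QTcF. Their only sample-size figure is the original power above 90% for NASH resolution (35% vs 15%, 100 vs 100, two-sided 5%). It reproduces at 91.0%, but it does not bear on this point.

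**Inputs.**
- N about 55, allocation 2:1:2:1 (Protocol 9.2). Each dose: 55 × 2/6 = 18.3. Pooled placebo: 55 × (1+1)/6 = 18.3. Use 18 vs 18.
- Assumed, not in the documents: heart-rate SD s = 10 bpm at baseline and after, and correlation r between the two of 0.4 to 0.7.
- t with 34 df, 97.5% point: 2.032.

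**Formulas.**
- Unadjusted: SD of change = s√(2(1−r)).
- Baseline-adjusted: residual SD = s√(1−r²).
- SE of the difference = SD × √(1/18 + 1/18) = SD/3. Half-width = 2.032 × SE.

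| r | Change SD | SE | Half-width, unadjusted | Residual SD | SE | Half-width, adjusted | Narrower by |
|---|---|---|---|---|---|---|---|
| 0.4 | 10.95 | 3.65 | 7.4 bpm | 9.17 | 3.06 | 6.2 bpm | 16% |
| 0.7 | 7.75 | 2.58 | 5.2 bpm | 7.14 | 2.38 | 4.8 bpm | 8% |

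The last column is 1 − √((1+r)/2). The same gain expressed as variance is 1 − (1+r)/2, or 30% at r = 0.4 and 15% at r = 0.7.

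**Is chance baseline imbalance a further error?** Its SD is 10 × √(2/18) = 3.33 bpm. The part carried into the raw change difference is (1−r) × 3.33, which is 2.0 bpm at r = 0.4 and 1.0 bpm at r = 0.7. At r = 0.4 the unadjusted variance is 3.65² = 13.3 and the adjusted variance is 3.06² = 9.3; the gap of 4.0 equals 2.0². At r = 0.7 it is 6.7 − 5.7 = 1.0 = 1.0². The carried imbalance is therefore the whole of the precision gain, counted once. It is not an extra bias.

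**Range over other assumptions, 18 vs 18.**
- Heart rate, change SD 6 to 12 bpm: half-width 4.1 to 8.1 bpm unadjusted, 3.5 to 7.0 bpm adjusted at r = 0.5.
- QTcF, change SD 10, 15 and 20 ms: 6.8, 10.2 and 13.5 ms unadjusted; 5.9, 8.8 and 11.7 ms adjusted at r = 0.5.
- Against one matched placebo group (18 vs 9) with heart-rate change SD 10 bpm, the unadjusted half-width is 8.4 bpm rather than 6.8 bpm, so the comparator needs to be named.

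These are single-visit, complete-data approximations. An MMRM with missing visits will differ somewhat.

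**The case against.** The strongest reply is that this is declared design. Protocol 9.4.1 and SAP 3.3 say that treatments are compared in tables with descriptive statistics, so side-by-side columns satisfy Protocol 9.1. That stands: nothing in the plan is breached.

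Second, the asymmetry is between objectives. SBP is modelled because it is also an efficacy endpoint; DBP, like heart rate, is descriptive only. That stands too. A reader might infer that the plan favours a hoped-for benefit over a known harm, but the documents show only that one parameter sits under two objectives.

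Third, a reader might infer that heart rate and QTcF get nothing but means, or that the effect cannot be read with its uncertainty. Neither is so. SDs, ranges, abnormality and threshold counts and AESI tables are planned, and a crude difference with its CI follows from n, mean and SD. The unadjusted half-widths above are that recoverable interval.

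Fourth, the documents do not call heart rate the main cardiovascular harm. Protocol 4.2.3.1 ties its particular cardiovascular focus to adjudicated events, and QT prolongation is only a potential risk.

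What the reply does not meet is the gap itself: a contrast against placebo is the primary question, and no output states one. Nor does the descriptive label exclude an interval. Protocol 9.4.2 already describes exploratory endpoints as analysed descriptively against placebo with 95% CIs, and Protocol 9.4.3 leaves room for exceptions.

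**Conclusion.** The point holds as a low-cost improvement, not as an error or a departure from the protocol. For heart rate and QTcF the SAP states no difference from placebo, no interval for one and no baseline adjustment. What is lost is a stated and somewhat more precise placebo-corrected estimate.

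The precision gain is modest: 8–16% in half-width for heart rate, on the assumed SD of 10 bpm and correlation of 0.4 to 0.7. The larger benefit is that the contrast, comparator and interval would be fixed in advance rather than assembled by each reader. The estimate would remain imprecise, at roughly ±5 to ±6 bpm adjusted on these assumptions, and it is not a powered test. The case is strongest for vital-sign heart rate. ECG heart rate and QTcF are reasonable as supportive analyses.

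**What to change.** In SAP 4.5.4.2 and 4.5.5.2, add the MMRM of SAP 4.2.3.4, in the safety set with on-treatment data and with that section's covariance fallbacks. Apply it to vital-sign heart rate and, as supportive analyses, to ECG heart rate and QTcF. Report the LS mean difference of each dose versus pooled placebo with a 95% CI by visit and no p-value, labelled descriptive. Write out the difference explicitly, because SAP 4.2.3.4 describes MMRM output by treatment and visit and does not spell out a contrast. If the data are already unblinded, label the analysis supplementary.

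The cost is a few extra model runs and no new data. Vital signs and ECG share the visit windows of SAP Table 3, and their baselines are defined in SAP 3.3.1.1. There are two downsides. Nine visits through Week 48 give an unstructured covariance 9 × 10/2 = 45 parameters for about 55 participants, so it may not converge and the fallbacks may be needed. The intervals will also be wide.
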